8.7 DEMOGRAPHICS, MEDICAL HISTORY, BASELINE CHARACTERISTICS, AND CONCOMITANT MEDICATIONS

Demographic data and other baseline characteristics, medical history, and concomitant **medications will be summarized by means of descriptive statistics. Where applicable**, comparisons among treatment groups will be performed using an analysis of variance (ANOVA) model for continuous variables and a Cochran-Mantel-Haenszel (CMH) test for categorical variables.

8.8 EFFICACY ANALYSES

8.8.1 Primary Efficacy Endpoint

The primary efficacy endpoint is the change from baseline in weekly SBM rate over the 4-week treatment period.

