8.2 SAMPLE SIZE AND POWER CONSIDERATIONS

Based on data from two phase 3 trials conducted by the sponsor in adults with IBS-C, consider the sample size necessary for observing a significant difference in the change from baseline in SBM frequency in Group B (the adolescents) since data from the adults is likely more applicable to Group B participants. Then, a study with a plecanatide group sample size of 102 and a placebo group sample size of 34 (representing 3:1 randomization, plecanatide to placebo) achieves 81.5% power at the 0.05% level of significance when the difference in mean change from baseline in weekly SBM frequency at four weeks is 1.5 and the placebo group and plecanatide group standard deviations are 2.3 and 3.5 respectively. Since study SP304202-14 is being conducted in children and adolescents with IBS-C, and the primary analysis of the primary endpoint will be an ANCOVA using a linear mixed-effects model, the sponsor believes that 30 patients per treatment group (placebo and 3 dose levels of plecanatide), yielding a planned target enrollment of a total of 210 patients (90 children and 120 adolescents), will prove sufficient for achieving the primary objective of this phase 2 study.

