8.4 GENERAL CONSIDERATIONS

The final data analysis will be performed after all patients have either completed or have been discontinued from the study. The study will be unblinded after patient membership in each of the various analysis populations has been determined at a blinded data review meeting and upon confirmation of database lock.

Three treatment groups are identified for all analyses cited in the following as “by treatment group”: A (patients in Age Group A receiving plecanatide doses of 0.5 mg or 1.0 mg); B (patients in Age Group B receiving plecanatide doses of 1.0 mg, 2.0 mg, or 3.0 mg); Placebo (all patients randomized to receive placebo.)

Any deviations from the analyses presented here will be detailed in the clinical study report. All outputs will be produced using SAS® version 9.2 or later.

All efficacy data will be summarized and analyzed using the FAS and PP Populations unless otherwise noted. Safety data will be summarized using the Safety Population.

Imputation of missing data, where appropriate, will be performed as indicated for a given analysis. Any spurious or erroneous data will be queried and followed up until satisfactorily resolved; if not resolvable, the data will be set to missing. All data collected in the clinical database will be included in the data listings.

Summary statistics—number of patients (n), mean, standard deviation (SD), median, minimum, and maximum—will be presented for continuous variables. Frequencies and percentages will be presented for categorical variables. Unless otherwise noted, percentages will be calculated using the total number of patients in the appropriate population and/or subgroup and per treatment group where applicable. Where data are collected over time, both the observed data and change from the Screening Period (baseline) will be summarized at each time point.

Statistical testing including p-values and confidence intervals (CIs) will be presented as described in each section below. The Type I error rate (alpha) for the analysis of the primary efficacy endpoint is 0.05 (two-sided).

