8.8.1.1 Analysis of the Primary Efficacy Endpoint

The weekly SBM rate for each patient will be computed, as described in **Section 8.4.1**, for each week of the 4-week treatment period. The change from baseline in mean weekly SBM rate will be analyzed using a linear mixed-effects model with fixed effects for gender (stratification variable), treatment, week, and the corresponding baseline value; a random intercept for patient will also be specified. The least squares (LS) mean change from baseline will be presented, by treatment group, and the difference in LS means for each treatment group, A, B, and A and B combined, versus Placebo, with 95% confidence intervals and corresponding statistical *p*-values.

The above analysis will be repeated for the PP Population.

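### The only stated power (81.5%) is worded for the SBM difference at four weeks, while the primary endpoint and model concern the change over Weeks 1 to 4

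*Combined protocol and SAP*

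**What the plan says.** **Power statement.** Protocol 8.2, repeated in the synopsis and SAP 3.1, takes its inputs from two adult phase 3 trials. With 102 plecanatide and 34 placebo patients the design "achieves 81.5% power at the 0.05% level of significance". The effect assumed for that figure is worded as follows: "when the difference in mean change from baseline in weekly SBM frequency at four weeks is 1.5". For the spread, the section says that "the placebo group and plecanatide group standard deviations are 2.3 and 3.5 respectively". The section then mentions the paediatric population and the mixed-model ANCOVA, and records the sponsor's belief that 30 patients per arm are enough. It gives no power for that model or for that sample.

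**Endpoint.** Protocol 8.8.1: "The primary efficacy endpoint is the change from baseline in weekly SBM rate over the 4-week treatment period". The synopsis, Protocol 2.4.1.1 and SAP 5.2.1 also refer to the whole four weeks.

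**Model.** Protocol 8.8.1.1 computes the weekly SBM rate for each of the four weeks and fits a "linear mixed-effects model with fixed effects for gender (stratification variable), treatment, week, and the corresponding baseline value", plus a random patient intercept. There is no treatment-by-week term. SAP 5.2.2 adds that interaction, but it still reports LS mean differences by treatment group and names no Week 4 contrast as primary.

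**Elsewhere.** The Study Design part of the synopsis distinguishes change across the treatment period from change at its end. Protocol 8.8.2.2 makes SBM change by study week a secondary analysis.

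**The concern.** A difference at one time point and a difference in four-week means are different quantities with different SDs. The power statement is worded for the first and the primary analysis estimates the second. Averaging over weeks reduces the SD, which raises power. An effect that is smaller in the early weeks would make the four-week mean difference less than 1.5, which lowers power. The plan gives neither the four-week mean difference nor its SD, so the two influences cannot be netted off.

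This bears on the sample size because Protocol 8.2 moves from 102 versus 34 to 30 per arm (90 versus 30 in Group B) partly on the strength of the mixed model. Whether the repeated measures make up for the smaller sample is exactly what the stated figure does not tell the reader. Correcting the printed significance level or the group sizes would leave this question open.

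**Working it through.** **Inputs from the documents.** Difference 1.5; SDs 3.5 (plecanatide) and 2.3 (placebo); 102 versus 34 (Protocol 8.2). Two-sided alpha 0.05 (Protocol 8.4). The planned Group B sample is 3 × 30 = 90 active and 30 placebo (Protocol 6.2, Table 3).

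**1. The plan's figure.** Unequal-variance normal calculation:

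- SE = √(3.5²/102 + 2.3²/34) = √(0.1201 + 0.1556) = 0.525
- Power = Φ(1.5/0.525 − 1.960) = **81.5%**

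This matches the plan. Reading the printed 0.05% literally (alpha 0.0005) gives 26.6%, so 0.05 was evidently meant. The calculation is a plain two-sample comparison of one value per patient. It contains no weeks, no within-patient correlation and no baseline covariate.

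**2. The same inputs at the planned size.** SE = √(3.5²/90 + 2.3²/30) = √(0.1361 + 0.1763) = 0.559; power = Φ(1.5/0.559 − 1.960) = **76.5%**.

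**3. What the primary model estimates.** Without a treatment-by-week term, the protocol model has a single treatment effect common to Weeks 1 to 4. Protocol 8.4.1 sets a week with no recorded response to zero, so each patient contributes four values and the effect is in substance the baseline-adjusted difference in four-week means. The SAP model could supply a Week 4 contrast, but SAP 5.2.2 does not ask for one. For pain scores, SAP 5.2.4.1 does ask for each week as well as all four weeks together.

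**4. If 1.5, 2.3 and 3.5 are Week 4 values.** The following are assumptions, because the documents do not give them: equal SDs in each week, a common correlation ρ between a patient's weekly changes, and no gain from the covariate. The SD of the four-week mean is then the weekly SD × √((1 + 3ρ)/4).

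| ρ | SD factor | 102/34, mean diff. 1.5 | 102/34, 1.2 | 90/30, mean diff. 1.5 | 90/30, 1.2 | Break-even mean diff. |
|---|---|---|---|---|---|---|
| 0.3 | 0.689 | 98.6% | 91.2% | 97.3% | 87.6% | 1.03 |
| 0.5 | 0.791 | 95.1% | 82.4% | 92.4% | 77.5% | 1.19 |
| 0.7 | 0.880 | 90.1% | 73.8% | 86.2% | 68.4% | 1.32 |
| 0.9 | 0.962 | 84.4% | 66.1% | 79.7% | 60.7% | 1.44 |

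The 1.2 (20% below 1.5) is illustrative and has no source in the documents. The break-even is 1.5 × SD factor, the four-week mean difference at which power equals the single-time-point figure (81.5% at 102/34, 76.5% at 90/30). Above it the stated approach is conservative; below it, optimistic.

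**5. If they are already Weeks 1 to 4 means.** Steps 1 and 2 apply unchanged. The only corrections are the wording and the sample size, and the figure for 90 versus 30 is 76.5%.

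**The case against.** The wording may be loose. Protocol 8.2 never says Week 4 or Days 22 to 28. The adult phase 3 trials ran for 12 weeks (Protocol 2.1.5), so the phrase may only mean that those data were summarised through four weeks, to match this trial. The two-sample arithmetic is the same under either reading, so reproducing 81.5% does not decide between them. This stands, and it is why the first step is to ask what the inputs represent.

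Even if they are Week 4 values, the protocol's model assumes one effect in every week. Under that assumption 1.5 also serves as the mean difference, and 81.5% is conservative for 102 versus 34. Nothing in the documents describes a gradual SBM effect in adults. This also stands as far as it goes, but the SAP drops the common-effect assumption by adding the interaction.

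A reader might infer that the powered comparison is one the primary analysis never makes. That goes too far: SAP sections 5 and 5.2.2 do compare the combined Group B doses with Group B placebo, so only the time summary is in doubt. Week-by-week SBM results are also planned (Protocol 8.8.2.2 and the SAP 9.1 table list).

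Finally, the trial is declared exploratory, with no multiplicity adjustment (Protocol 8.8.4), and Protocol 8.2 does not expressly claim 81.5% for the mixed model. That limits the weight of the point. It does not supply the missing power.

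**Conclusion.** The point holds as a mismatch between the power statement and the primary endpoint. As written, the one power figure in the plan is not the power of the primary contrast, and the documents do not allow that power to be worked out.

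A reader might infer that the trial is underpowered for its primary endpoint because of the time point. The documents do not support this. Under the assumptions in step 4, power at 90 versus 30 is 79.7% to 97.3% if the four-week mean difference is also 1.5, and 60.7% to 87.6% if it is 1.2. Which applies depends on a mean difference and a correlation that are not given.

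The one figure that needs no outside assumption beyond the plan's own inputs is 76.5% at 90 versus 30, and that shortfall comes from the group sizes, not the time point.

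**What to change.** In the synopsis, Protocol 8.2 and SAP 3.1:

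1. State whether 1.5, 2.3 and 3.5 are Week 4 values or means over Weeks 1 to 4 in the adult trials.
2. If they are Week 4 values, replace them with the difference and SDs for the mean change over Weeks 1 to 4 from the same trials. Failing that, state an assumed mean difference and week-to-week correlation, with a range.
3. In either case, restate the power for Group B combined doses versus placebo at 90 versus 30. If the inputs are already Weeks 1 to 4 means, this is 76.5% by the same calculation.

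Endpoint, model and enrolment stay unchanged. The cost is a check of the source of the inputs, one recalculation and edits in three places. The downside is that the stated power may become less favourable.

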8.8.1.1 Analysis of the Primary Efficacy Endpoint

The weekly SBM rate for each patient will be computed, as described in **Section 8.4.1**, for each week of the 4-week treatment period. The change from baseline in mean weekly SBM rate will be analyzed using a linear mixed-effects model with fixed effects for gender (stratification variable), treatment, week, and the corresponding baseline value; a random intercept for patient will also be specified. The least squares (LS) mean change from baseline will be presented, by treatment group, and the difference in LS means for each treatment group, A, B, and A and B combined, versus Placebo, with 95% confidence intervals and corresponding statistical *p*-values.

The above analysis will be repeated for the PP Population.

8.8.2 Secondary Efficacy Endpoints

The secondary efficacy endpoints and methods of analysis are:

8.8.2.1 Change from Baseline in Frequency and Severity of Abdominal Pain and Abdominal Discomfort

The weekly abdominal pain and the weekly abdominal discomfort rate for each patient will be computed, as described in **Section 8.4.1**, for each week of the 4-week treatment period and for the two weeks of the follow-up period. A summary, by treatment group, of the mean weekly abdominal pain and abdominal discomfort rate and change from baseline in mean weekly abdominal pain and abdominal discomfort rates, for each of the 6 study weeks will be presented. The change from baseline in mean weekly abdominal pain and abdominal discomfort rates will be analyzed using a linear mixed-effects model with fixed effects for gender (stratification variable), treatment, week, the interaction of treatment and week, and the corresponding baseline value; a random intercept for patient will also be specified. The least squares (LS) mean change from baseline will be presented, by treatment group, and the difference in LS means for each treatment group, A, B, and A and B combined, versus Placebo, with 95% confidence intervals and corresponding statistical p-values.

The weekly average abdominal pain and abdominal discomfort scores will be determined using the approach defined in **Section 8.4.1** and presented for each week in the 4-week treatment period; the baseline weekly average is determined as described in **Section 8.4.3**. The change from baseline in the weekly averaged abdominal pain and abdominal discomfort scores will be analyzed in the FAS Population using a linear mixed-effects model with fixed effects for gender (stratification variable), treatment, week, the interaction of treatment and week, and the corresponding baseline value, and a random intercept for patient. Least Squares (LS) means, with 95% confidence intervals and the corresponding statistical p-value, will be presented for each week, and across all 4 weeks, of the 4-week treatment period for the difference in LS means for each treatment group, A, B, and A and B combined, versus Placebo. The analysis of interest for this secondary endpoint is the difference in LS means between each plecanatide group (A, B, and A and B combined) versus placebo for the estimated overall average change from baseline in abdominal pain and abdominal discomfort scores across the 4-week treatment period.

8.8.2.2 Change from Baseline in Frequency of BMs, SBMs, and CSBMs, by Study Week

The weekly BM rate for each patient will be computed, as described in **Section 8.4.1**, for each week of the 4-week treatment period and for the two weeks of the follow-up period. A summary, by treatment group, of the mean weekly BM rate, and change from baseline in mean weekly BM rate, for each of the 6 study weeks will be presented. The change from baseline in mean weekly BM rate will be analyzed using a linear mixed-effects model with fixed effects for gender (stratification variable), treatment, week, the interaction of treatment and week, and the corresponding baseline value; a random intercept for patient will also be specified. The least squares (LS) mean change from baseline will be presented, by treatment group, and the difference in LS means for each treatment group, A, B, and A and B combined, versus Placebo, with 95% confidence intervals and corresponding statistical p-values.

Similarly, for the change from baseline in frequency of SBMs and CSBMs by study week.

8.8.2.3 Time to First BM

For the time to first BM endpoint, the distribution for each treatment arm will be estimated by the Kaplan-Meier method and will be compared by the Log-rank test. The median time along with the 95% confidence

limits for the median will be presented for each treatment arm. Simultaneous confidence bounds for the Kaplan-Meier curve will be computed for all treatment groups.

8.8.2.4 Change from Baseline in Stool Consistency (mBSFS-C or BSFS)

Stool consistency for a bowel movement is measured using the mBSFS-C for patients in Group A and the BSFS for patients in Group B. The weekly average stool consistency scores will be determined using the approach defined in **Section 8.4.1** and presented for each week in the 4-week treatment period; the baseline weekly average is determined as described in **Section 8.4.3**. The change from baseline in the average weekly stool consistency score will be analyzed in the FAS Population using a linear mixed-effects model with fixed effects for gender (stratification variable), treatment, week, the interaction of treatment and week, and the corresponding baseline value, and a random intercept for patient. Least Squares (LS) means, with 95% confidence intervals and the corresponding statistical p-value, will be presented for each week, and across all 4 weeks, of the 4-week treatment period for the difference between the difference in LS means for each of treatment groups A and B versus Placebo. The analysis of interest for this secondary endpoint is the difference in LS means between each plecanatide group and placebo for the estimated overall average change from baseline across the 4-week treatment period.

The above analysis will be repeated for the PP Population.

8.8.2.5 Use of Rescue Medication

The number of tablets of rescue medication used per week, and overall, for the 4-week treatment period will be analyzed by treatment group. The Mann Whitney U Test (Wilcoxon Rank Sum Test) will be used to compare the difference between each treatment group, A, B, and A and B combined, versus Placebo at each week, and over all 4 weeks, of the 4-week treatment period.

8.8.2.6 Change from Baseline in Frequency of Fecal Incontinence

The weekly fecal incontinence rate for each patient will be computed, as described in **Section 8.4.1**, for each week of the 4-week treatment period and for the two weeks of the follow-up period. A summary, by treatment group, of the mean weekly fecal incontinence rate, and change from baseline in mean weekly fecal incontinence rate, for each of the 6 study weeks will be presented. The change from baseline in mean weekly fecal incontinence rate will be analyzed using a linear mixed-effects model with fixed effects for gender (stratification variable), treatment, week, the interaction of treatment and week, and the corresponding baseline value; a random intercept for patient will also be specified. The least squares (LS) mean change from baseline will be presented, by treatment group, and the difference in LS means for each treatment group, A, B, and A and B combined, versus Placebo, with 95% confidence intervals and corresponding statistical p-values.

8.8.2.7 Change from Baseline in Frequency and Severity of Defecation Pain

The weekly defecation pain rate for each patient will be computed, as described in **Section 8.4.1**, for each week of the 4-week treatment period and for the two weeks of the follow-up period. A summary, by treatment group, of the mean weekly defecation pain rate, and change from baseline in mean weekly defecation pain rate, for each of the 6 study weeks will be presented. The change from baseline in mean weekly defecation pain rate will be analyzed using a linear mixed-effects model with fixed effects for gender (stratification variable), treatment, week, the interaction of treatment and week, and the corresponding baseline value; a random intercept for patient will also be specified. The least squares (LS) mean change from baseline will be presented, by treatment group, and the difference in LS means for each treatment group, A, B, and A and B combined, versus Placebo, with 95% confidence intervals and corresponding statistical p-values.

The weekly average defecation pain score will be determined using the approach defined in **Section 8.4.1** and presented for each week in the 4-week treatment period; the baseline weekly average is determined as described in **Section 8.4.3**. The change from baseline in the weekly averaged defecation pain score will be analyzed in the FAS Population using a linear mixed-effects model with fixed effects for gender (stratification variable), treatment, week, the interaction of treatment and week, and the corresponding baseline value, and a random intercept for patient. Least Squares (LS) means, with 95% confidence intervals and the corresponding statistical p-value, will be presented for each week, and across all 4 weeks, of the 4-week treatment period for the difference in LS means for each treatment group, A, B, and A and B combined, versus Placebo. The analysis of interest for this secondary endpoint is the difference in LS means between each plecanatide group (A, B, and A and B combined) versus placebo for the estimated overall average change from baseline in abdominal pain and abdominal discomfort scores across the 4-week treatment period.

8.8.2.8 Change from Baseline in Frequency of Large Diameter Stools

The weekly large diameter stools rate for each patient will be computed, as described in **Section 8.4.1**, for each week of the 4-week treatment period and for the two weeks of the follow-up period. A summary, by treatment group, of the mean weekly large diameter stools rate, and change from baseline in mean weekly large diameter stools rate, for each of the 6 study weeks will be presented. The change from baseline in mean weekly large diameter stools rate will be analyzed using a linear mixed-effects model with fixed effects for gender (stratification variable), treatment, week, the interaction of treatment and week, and the corresponding baseline value; a random intercept for patient will also be specified. The least squares (LS) mean change from baseline will be presented, by treatment group, and the difference in LS means for each treatment group, A, B, and A and B combined, versus Placebo, with 95% confidence intervals and corresponding statistical p-values.

8.8.3 Patient Reported Outcomes (PRO)

PRO questionnaire data for IBS Disease Severity, Health-Related Quality of Life, Patient Global Rating of Change—IBS Symptoms, Patient Global Rating of Change—IBS Abdominal Pain, Treatment Continuation and Treatment Satisfaction Assessments will be included in the patient listings (**Appendix I**). Summary analyses of these data will also be provided as described in the SAP.

